11.2.2 Adverse Events of Special Interest

The Adverse Events of Special Interests (AESI) categories will be summarized and presented for each treatment group using SMQ/CMQ.

| AESI | Type of MedDRA Query | Broad or Narrow Search | SMQ/CMQ Search Criteria |
|--|----------------------|------------------------|---|
| Infection | CMQ | | "Infection" |
| Serious Infection | CMQ | | "Infection" – Subset for SAEs |
| Opportunistic Infection | CMQ | | "Opportunistic infection" |
| Herpes zoster | CMQ | | "Herpes zoster" |
| Tuberculosis | CMQ | | "Tuberculosis" |
| Malignancy | SMQ | Narrow | "Malignancies," "Malignant lymphomas" |
| Non-Melanoma Skin Cancer (NMSC) | SMQ | Narrow | "Skin neoplasms, malignant and unspecified" |
| Malignancy other than NMSC | | | |
| Hepatic Disorder | SMQ | Narrow | "Drug Related Hepatic disorders" |
| Gastrointestinal Perforations | SMQ | Narrow | "Gastrointestinal perforation" |
| Anemia | CMQ | | "Non-Hemolytic and Non-Aplastic anemias" |
| Adjudicated Cardiovascular Events | Output from CAC | | |
| Neutropenia | CMQ | | "Hematological toxicity – Neutropenia" |
| Increased serum creatinine and renal dysfunction | SMQ | Narrow | "Acute renal failure" |
| Elevated creatine phosphokinase | SMQ | Narrow | "Rhabdomyolysis/myopathy" |

Additional AEs may be considered for tabulation/summary based on recommendations from Clinical and Safety as deemed appropriate.

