### **8.1.7.2 Analysis of Adverse Events**

#### **8.1.7.2.1 Treatment-Emergent Adverse Events**

Adverse events (AEs) will be coded using the Medical Dictionary for Regulatory Activities (MedDRA) dictionary. Treatment-emergent adverse events, defined as AEs that began or worsened in severity after initiation of study drug in each period of the study, will be tabulated by system organ class (SOC) and MedDRA preferred term for each treatment group.

Adverse events starting more than 30 days following discontinuation of study drug will not be included in summaries of treatment-emergent AEs. When summarizing adverse events by relationship or severity, if a subject has an event with unknown severity or relationship then the subject will be counted in the severity/relationship category of "unknown" even if the subject has a second occurrence of the same event with a severity/relationship present. The only exception is if the subject has a second occurrence of the same event with the most extreme severity (i.e., "severe") or a relationship categories of "reasonable possibility." In this case, the subject will be counted under these most extreme severity/relationship categories.

Subjects reporting more than one AE for a given MedDRA preferred term will be counted only once for that term using the most severe incident in each study period. Subjects reporting more than one type of event within an SOC will be counted only once for that SOC.

Frequencies and percentages of subjects with treatment-emergent AEs will be summarized for each treatment group as follows:

- Any event
- By system organ class, and preferred term
- By system organ class, preferred term and maximum relationship
- By system organ class, preferred term and maximum severity
- Any event and by system organ class and preferred term for events resulting in death
- Any event and by system organ class and preferred term for events resulting in study drug discontinuation
- Any event and by system organ class and preferred term for serious events
- Any event and by system organ class and preferred term for adverse events with a relationship of "reasonable possibility"
- Any event and by system organ class and preferred term for adverse events of special interest (infection, opportunistic infection, and gastrointestinal perforations, malignancies and drug related hepatic disorders)

All AEs leading to early termination of study drug will be presented in listing format.

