Frequencies and percentages for any AE and for each preferred term will be compared between each of the ABT-494 dosing groups and the placebo group using a Fisher's exact test.

The adverse events of special interest (infection, opportunistic infection, and gastrointestinal perforations, malignancies and drug related hepatic disorders) will be specified in the SAP.

A listing by treatment group of treatment-emergent AEs grouped by SOC and MedDRA preferred term with subject ID numbers will be generated.

The post-treatment AEs will be summarized in the same way as the treatment-emergent AEs described above.

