11.2.2 Adverse Events of Special Interest

The Adverse Events of Special Interests (AESI) categories will be summarized and presented for each treatment group using SMQ/CMQ/LMQ/Preferred Term.

| AESI | Type of MedDRA Query | Broad or Narrow Search | SMQ/CMQ/LMQ Search Criteria |
|--|----------------------|------------------------|---|
| Serious Infections | CMQ | | "Infection" – Subset for SAEs |
| Opportunistic Infection | CMQ | | "Opportunistic infection" |
| Herpes zoster | CMQ | | "Herpes zoster" |
| Tuberculosis | CMQ | | "Tuberculosis" |
| Malignancy | SMQ | Narrow | "Malignancies," |
| Non-Melanoma Skin Cancer (NMSC) | SMQ | Broad | Skin Malignant tumours (Broad SMQ) removing Melanoma CMQ |
| Malignancy other than NMSC | SMQ | Narrow | Malignancy and removing NMSC output |
| Lymphoma | SMQ | | "Malignant Lymphomas" |
| Hepatic Disorder | SMQ | Narrow | "Drug Related Hepatic disorders" |
| Intestinal Perforations | LMQ | | Terms for/related to any part of GI Tract, GI Ulcers, obstruction, hemorrhage |
| Anemia | CMQ | | "Non-Hemolytic and Non-Aplastic anemias" |
| Adjudicated Cardiovascular Events | Output from CAC | | |
| Neutropenia | CMQ | | "Hematological toxicity – Neutropenia" |
| Lymphopenia | CMQ | | "Hematological Toxicity – Lymphopenia (Veliparib Product Specific)" |
| Renal dysfunction | SMQ | Narrow | "Acute renal failure" |
| Rhabdomyolysis/myopathy | SMQ | Narrow | "Rhabdomyolysis/Myopathy" |
| Creatine phosphokinase (CPK) Elevation | Preferred Term | | "blood creatine phosphokinase increased" |

Additional AEs may be considered for tabulation/summary based on recommendations from Clinical and Safety as deemed appropriate.

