11.2 Analysis of Adverse Events

11.2.1 Treatment-Emergent Adverse Events

Treatment-emergent AEs for double-blind Induction period are defined as events that begin or worsen either on or after the first dose of the study medication and within 30 days after the last dose of the study medication for who subjects who discontinued study prior to double-blind Extension Period or up to the first dose of double-blind Extension Period for subjects who received at least a dose of study medication during double-blind extension period. An overview of treatment-emergent AEs, including AEs of special interest such as adverse events leading to death and adverse events leading to early termination, AEs by Medical Dictionary for Drug Regulatory Activities (MedDRA version 18.1 or later) preferred term and system organ class, AEs by maximum relationship to study drug, and AEs by maximum severity will be summarized by number and percentage. Treatment group differences (each ABT-494 dose group versus placebo group, as well as ABT-494 dose groups combined versus placebo group) in the overall incidence of treatment-emergent AEs will be assessed with Fisher's exact test for each preferred term for double-blind induction period.

Changes in laboratory data will be described using statistical characteristics and compared between treatment groups and placebo will be performed using a one-way Analysis of Variance (ANOVA). In addition, shift tables and listings will be provided for abnormal values, whereby the normal range of the analyzing laboratory will be used. Vital signs will be analyzed similarly.

The number and percent of subjects experiencing treatment-emergent adverse events will be summarized for the following adverse event categories. Comparisons of the percent of subjects experiencing an adverse event between treatment groups and placebo will be

performed using Fisher's exact tests. Only P values < 0.100 when rounded to three digits will be presented.

- Any treatment-emergent adverse event.
- Any treatment-emergent adverse event that was rated as possibly related to study drug by the investigator (Reasonable Possibility).
- Any treatment-emergent severe adverse event.
- Any treatment-emergent serious adverse event.
- Any treatment-emergent adverse event leading to discontinuation of study drug.
- Any treatment-emergent adverse event leading to death.
- Any treatment-emergent adverse event of special interest.

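### The Induction SAP's non-melanoma skin cancer category has no melanoma removal, so by the title of its query a melanoma would be counted there (minor)

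*SAP*

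**What the plan says.** The SAP file holds two plans, one for induction and one for the extension phase. Protocol section 8.1.7.2.1 names malignancy among the adverse events of special interest but gives no search terms. It leaves them to the SAP: "malignancies and drug related hepatic disorders) will be specified in the SAP".

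Three rows of the table in Induction SAP section 11.2.2 matter here:

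- Overall malignancy: "Malignancy | SMQ | Narrow | 'Malignancies,' 'Malignant lymphomas".
- Non-melanoma skin cancer: "Non-Melanoma Skin Cancer (NMSC) | SMQ | Narrow | 'Skin neoplasms, malignant and unspecified".
- "Malignancy other than NMSC": a label only. The text available shows no query type, scope or criterion.

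Extension SAP section 11.2.2 builds the same two subcategories differently. Non-melanoma skin cancer is "Skin Malignant tumours (Broad SMQ) removing Melanoma CMQ", and the companion row is "Malignancy and removing NMSC output".

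**The concern.** The label and the search rule of the induction row disagree. The label excludes melanoma. The rule is a query for malignant and unspecified skin neoplasms, with nothing subtracted.

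The protocol treats these two groups of tumour differently. Section 5.4.1 requires withdrawal for malignancy but spares localized non-melanoma skin cancer. Exclusion criterion 28 bars earlier malignancy but tolerates treated, non-metastatic squamous or basal cell skin carcinoma. A melanoma reported as non-melanoma would therefore sit in the category that the protocol treats as less serious. Section 3.2 of the protocol lists malignancy among the open safety questions for a non-selective JAK inhibitor, and induction is the only placebo-controlled period of the trial.

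**Working it through.** The plan gives no figure on this point to reproduce. The check has three parts.

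**1. Does the rule admit what the label excludes?**
- By its title, the induction query covers malignant skin neoplasms.
- A melanoma is a malignant skin neoplasm, and nothing in the description of a narrow search excludes one.
- Neither the row, the rest of the table nor the surrounding text of the Induction SAP removes melanoma. The closing sentence of section 11.2.2, which allows further events to be tabulated, adds categories and does not redefine this one.
- The Extension SAP does not reach back. Its section 3.0 says that induction was analysed separately under a SAP signed off before the December 2016 database lock.

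On the title, then, a melanoma falls in the row.

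**2. Which outputs would change?**

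| Output | Effect of one melanoma |
|---|---|
| Non-melanoma skin cancer row | Gains one subject wrongly |
| Companion row, malignancy other than non-melanoma skin cancer | Undefined in the Induction SAP; loses the subject only if derived by subtraction |
| Overall malignancy | Unchanged, by the query titles |
| Any event of special interest (Fisher's exact test, Induction SAP 11.2.1) | Unchanged, because the subject already counts through overall malignancy |
| Preferred-term tables and by-subject listing (Induction SAP 11.2.1) | Unchanged; they show the actual term |
| Cumulative Any ABT-494 tables (Extension SAP 5.1 and 11.2.1) | Show the actual term for events on active drug |

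**3. How large, and how likely?**

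Inputs: about 210 subjects, 35 per arm (protocol 8.2), and 16 weeks = 112 days of induction (protocol 5.1). The documents give no melanoma rate, so I assume 0.02 to 0.2 per 100 patient-years.

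- Misplacement per case: 1/35 = 2.9% in the affected arm, where 0 is correct.
- Maximum on-treatment exposure, if every subject completes induction: 210 × 112 / 365.25 = 64.4 patient-years. Per arm: 35 × 112 / 365.25 = 10.7.
- Expected cases = rate / 100 × 64.4. Chance of at least one = 1 − exp(−expected).

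| Assumed rate per 100 patient-years | Expected cases | Chance of at least one |
|---|---|---|
| 0.02 | 0.013 | 1.3% |
| 0.05 | 0.032 | 3.2% |
| 0.1 | 0.064 | 6.2% |
| 0.2 | 0.129 | 12.1% |

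Exclusion criterion 28 keeps out anyone with a previous melanoma, which points to the lower end.

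**The case against.** The strongest objection is that the claim depends on a term list nobody can see here. Whether a melanoma term belongs to the narrow search cannot be verified from the documents. A reader might take the melanoma subtraction in the Extension SAP as proof that the induction query holds melanoma terms. It is not proof: that step is applied to a query with another name and a broad scope. It is consistent with the title-based reading and shows that the sponsor has a melanoma list to subtract. This objection stands as a limit on certainty. It does not remove the conflict between label and rule.

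A reader might also infer that a melanoma would vanish from the companion row, which would read 0 instead of 1/35. The Induction SAP states no rule for that row. The loss follows only if the Extension SAP's subtraction is borrowed, and the induction plan does not say so.

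A third tempting step is to add a 30-day tail to everyone's exposure, giving 210 × 142 / 365.25 = 81.6 patient-years and a chance of up to 15%. Induction SAP section 11.2.1 does not support this. The period "within 30 days after the last dose of the study medication" applies to subjects who stopped before the extension. For those dosed in the extension, the induction window closes at the first extension dose. Subjects who stopped early also contribute less treatment time.

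Finally, one can say that almost nothing depends on this: most likely no case occurs, and the true term would be visible elsewhere. That is right, and it is why the point is minor.

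**Conclusion.** The point holds as a minor definition error. Judged by its query title, the induction row would count a melanoma under a non-melanoma label, and no other induction text corrects it. Each case misplaces one subject, 2.9% of an arm of 35, in a descriptive subcategory. The chance that any case arises is about 1.3% to 12%, more likely near the lower figure.

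This rests on three assumptions: that the query's content matches its title, that the melanoma rate lies in the assumed range, and that exposure is at the full-completion maximum of about 64 patient-years. A reader might infer that the malignancy signal as a whole is compromised. The documents do not support that: no efficacy result and no planned adverse-event comparison changes. Confidence is medium, because the term list is not available.

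**What to change.** In Induction SAP section 11.2.2:

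- Add the removal of melanoma terms (the Melanoma CMQ that the Extension SAP already uses) to the non-melanoma skin cancer row, and keep the narrow search.
- Fill in the companion row as SMQ, narrow, overall malignancy minus the corrected non-melanoma skin cancer output.

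This touches four table cells and needs no new data. Since the Induction SAP is signed off, record the change as a SAP clarification or as a note in the study report.

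It corrects the placement of melanoma only. By its title, the query would still bring in unspecified skin neoplasms. The two SAPs would still use different skin queries and different minimum MedDRA versions (18.1 for induction, 20.0 for extension), so their skin cancer rows should not be compared directly.

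### Two special-interest event searches in the Induction SAP do not match their labels and a third row has no search, so these rows may be misclassified and are not like for like with the Extension SAP

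*SAP*

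**What the plan says.** Protocol 8.1.7.2.1 names the special-interest events as "infection, opportunistic infection, and gastrointestinal perforations, malignancies and drug related hepatic disorders" and leaves their specification to the SAP. The two SAPs specify them in their sections 11.2.2 as follows, for the rows that matter here.

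| Category | Induction SAP | Extension SAP |
|---|---|---|
| Non-melanoma skin cancer (NMSC) | Narrow SMQ, "Skin neoplasms, malignant and unspecified"; no melanoma removal stated | Broad SMQ, "Skin Malignant tumours (Broad SMQ) removing Melanoma CMQ" |
| "Malignancy other than NMSC" | Query type, scope and criteria all empty | Narrow SMQ, "Malignancy and removing NMSC output" |
| CPK elevation | Labelled "Elevated creatine phosphokinase"; narrow rhabdomyolysis/myopathy SMQ only | Preferred term "blood creatine phosphokinase increased" |
| Rhabdomyolysis/myopathy | No row of its own | Own row, the same narrow SMQ |
| Infection, all | Own row | No row; serious infections, opportunistic infection, herpes zoster and tuberculosis only |

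Induction SAP 11.2.1 has an overview line for any special-interest event. It is compared with placebo by Fisher's exact test, and P values are shown only when below 0.100. Extension SAP 5.1 and 11.2.1 plan a cumulative adverse event overview from the induction baseline for everyone who received ABT-494.

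**The concern.** A reader of a special-interest table relies on the row labels. In the Induction SAP the CPK label and its search describe different things, the NMSC label promises an exclusion that the search does not state, and the complementary malignancy row cannot be programmed as written. The sponsor's later plan changes all three, which suggests that the distinctions were thought to matter.

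Induction is the only period with a placebo arm, so a category that is misdefined there cannot be checked against placebo later. If the empty row is filled by subtraction, as in the extension, a melanoma captured under NMSC would leave the row meant to hold it. A subject whose only relevant report is a raised CPK might appear neither in the CPK row nor in the any-special-interest line.

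In the other direction, the extension table omits a category that the protocol names. Extension SAP 12.1, which sets out differences from the protocol, lists efficacy variables only.

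**Working it through.** The documents state no count, rate or power for these events, so there is no figure to reproduce. The check is a comparison of the two tables, followed by a calculation for scale.

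**1. CPK.** The Extension SAP gives the rhabdomyolysis/myopathy SMQ a row under its own name and finds CPK elevation by a separate preferred term. The Induction SAP uses that same SMQ under the CPK label. On the sponsor's own later classification, the induction row is a rhabdomyolysis/myopathy row with a CPK label.

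**2. NMSC and its complement.** By its name the induction query covers malignant and unspecified skin neoplasms. Nothing in the row takes melanoma out, whereas the extension row does so explicitly. The complement depends on the NMSC definition, and in the Induction SAP it has no definition at all.

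**3. Infection.** The protocol names it, the Induction SAP tabulates it and the Extension SAP does not. A non-serious infection that is neither opportunistic, zoster nor tuberculosis counts as a special-interest event in induction but not in the extension. The any-special-interest line therefore has different content in the two phases.

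**4. What reaches the any-special-interest line in induction.** A melanoma placed in the wrong malignancy row should still count in that line through the overall malignancy row. A raised CPK outside the rhabdomyolysis/myopathy query would not count, unless the subject had another qualifying event. The CPK definition is therefore the one that chiefly bears on the placebo comparison.

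**5. Scale.** Inputs: 35 subjects per arm (Induction SAP 4.3; 210/6) and 5 × 35 = 175 on active drug. One subject is 1/35 = 2.9% of an arm, or 1/175 = 0.6% of the active arms combined. With *k* events in one active arm and none on placebo, the two-sided Fisher P is 2 × C(35,*k*)/C(70,*k*):

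- *k* = 1: 2 × 35/70 = 1.000
- *k* = 4: 2 × 52,360/916,895 = 0.114
- *k* = 5: 2 × 324,632/12,103,014 = 0.054

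For the combined active arms against 0/35, the two-sided Fisher P is 0.133 at 14 events and 0.081 at 15.

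The documents give no rate of CPK reports. Taking 1%, 5% and 10% as pure assumptions, the expected numbers among 175 are 1.75, 8.75 and 17.5. One isolated misplaced event would not produce a displayed P value. A missed cluster of CPK reports could, but only towards the top of that assumed range for the combined arms, or if the reports gathered in one dose group.

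**The case against.** The best opposing case is that little depends on these rows, and much of it stands.

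- **Stronger reading: the induction counts are wrong.** A reader might infer this, but the documents do not show it. They do not list what either query returns. The extension table is indirect evidence, and a count changes only if such an event occurs.
- **Stronger reading: CPK reports are missed where placebo is available and then look new in the extension.** Induction SAP 11.2.1 tests each preferred term against placebo, for each dose and all doses combined, and provides a by-subject listing. CPK is in the chemistry panel (protocol Table 2), so Induction SAP 11.3 compares its change from baseline with placebo and gives shift tables. This reading fails.
- **Stronger reading: bias between arms.** The same search applies to every arm, so no bias is shown.
- **A melanoma would disappear.** It should still appear in the overall malignancy row, the preferred-term tables and the listings. The loss from the complementary row depends on a subtraction that the Induction SAP does not state.
- **Comparability across phases has no formal use.** No induction-versus-extension test of these events is planned, and the cumulative overview would most naturally follow the Extension SAP's own table.
- **The protocol leaves specification to the SAP.** That is true, and it names neither CPK nor NMSC separately. Leaving out infection, however, goes beyond specifying a category that the protocol names.

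What remains is a stated search that does not measure its label and that feeds a line tested against placebo. The laboratory tables do not fully replace the event row. Under protocol 6.1.1.1 a laboratory abnormality becomes an adverse event only in limited circumstances, so the two measure different things.

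**Conclusion.** The point holds as a defect in how special-interest events are defined and labelled, with the consequence limited to possible misclassification. Events in the induction CPK, NMSC and other-malignancy rows, and in the any-special-interest line, may be misclassified. Rows with the same name cannot be read across the two phases. An induction event could be classed one way in the induction tables and another way in the cumulative overview. The documents do not support saying that counts are wrong, that events are lost or that arms are treated differently.

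No numerical size can be given. For CPK, what is at stake is every induction report coded only to the preferred term for raised CPK and not returned by the rhabdomyolysis/myopathy query. For skin cancer, few events are to be expected in 210 subjects over 16 weeks. The co-primary analyses, sample size and alpha are untouched. This is worth correcting, but it is a matter of safety reporting.

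The conclusion assumes that the queries return what their names suggest, and that the empty cells are empty in the signed document.

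**What to change.** Extension SAP section 3.0 says that the Induction SAP was signed before the December 2016 lock and that the induction analysis was performed. The induction change therefore belongs in a supplementary tabulation labelled as post hoc. Induction SAP 11.2.2 already allows additional event tabulations. In it:

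- use one query set and one MedDRA version for both phases (the SAPs now cite 18.1 or later and 20.0 or later);
- give rhabdomyolysis/myopathy its own label and add a CPK row by the preferred term "blood creatine phosphokinase increased";
- remove melanoma from NMSC, and say whether neoplasms of unspecified nature count, since the Extension SAP's search is broad and the documents do not show that it excludes them;
- define "Malignancy other than NMSC" as malignancy minus the NMSC output.

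In the Extension SAP, restore infection as a category in 11.2.2, and state that this one query set governs induction-period events in the cumulative overview.

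The cost is a few extra standard queries and one table per phase. The drawback is that the induction retabulation is post hoc and will stand beside the original rows, so each table must say which definitions it uses.

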The second generation of JAK inhibitors currently in development display varying potency and selectivity directed at members of the JAK family. Tofacitinib is a non-selective JAK inhibitor targeting JAK1, JAK2 and JAK3, but most potently inhibits JAK3. Although tofacitinib improves the clinical signs and symptoms of RA, questions remain surrounding the safety profile regarding apparent increases in the incidences of serious infection, malignancies, herpes zoster, and hematologic adverse events.

Tofacitinib has also been associated with reduced levels of hemoglobin, absolute lymphocytes counts, and total white blood cell counts in some subjects and also increased serum creatinine; total cholesterol, LDL cholesterol (LDL-C), and HDL cholesterol (HDL-C); and liver transaminases (ALT and AST). The increases in serum creatinine, lipids, and liver transaminase values typically have been asymptomatic, reversible, and were not associated with any overt declines in renal or hepatic function.

ABT-494 is a novel JAK1 selective inhibitor with minimal inhibitory effects on JAK2 and JAK3, which could potentially minimize some of the reported safety concerns with non-selective JAK inhibition which are thought to be mediated by inhibition of JAK2 and JAK3 signaling pathways. We propose to initiate a Phase 2 study in CD subjects with multiple doses of ABT-494 based on the following supportive findings: 1) demonstrated improved potency of ABT-494 versus tofacitinib in preclinical models of inflammation; 2) confirmed JAK1 selectivity of ABT-494 in both preclinical and clinical settings; 3) acceptable preclinical toxicological findings in chronic toxicity studies in two species; 4) acceptable safety and tolerability profile of ABT-494 in single ascending dose (SAD) and multiple ascending dose (MAD) studies in healthy volunteers and 5) evidence that JAK inhibition in preclinical models of inflammatory bowel disease results in clinical and endoscopic improvement. The current Phase 2 Study M13-740 will assess the benefit to risk profile of ABT-494 in CD subjects who have had an insufficient clinical response to anti-TNF therapies.

ABT-494 is a potent JAK1 selective inhibition that has been associated with endoscopic improvement and healing of the intestinal mucosa in preclinical animal models. More recently, filgotinib, a JAK1 inhibitor in Phase 2 clinical development in Crohn's disease

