### **5.5.3            Method of Assigning Subjects to Treatment Groups**

All subjects will be centrally randomized using an Interactive Response Technology (IRT). Before the study is initiated, the telephone number and call-in directions for the IRT will be provided to each site.

All subjects will be assigned a unique identification number by the IRT at the Screening Visit. Subjects who meet the inclusion and none of the exclusion criteria defined in Section 5.2.1 and Section 5.2.2 will be centrally randomized 1:1:1:1:1:1 to one of six treatment groups at Baseline (Week 0) in a double-blind manner. The IRT will assign a randomization number that will encode the subject's treatment group assignment according to the randomization schedule generated by the Statistics Department at AbbVie.

IRT will provide the appropriate medication kit number(s) to dispense to each subject. Study drug will be administered at the study visits as summarized in Section 5.5. Returned study medication should not be re-dispensed to any subject.

At Week 16, all subjects will be re-randomized in a ratio of 1:1:1 to the three double-blind doses of ABT-494 (3 mg BID, 6 mg BID or 12 mg BID). The subjects who were re-randomized at Week 16 to ABT-494 24 mg QD prior to Protocol Amendment 2 will continue to receive the same double-blind dose until Week 52/PD.

The re-randomization will be stratified by the induction dose received during the first 16 weeks and by response status (responder versus non-responder) at Week 16. All subjects will keep the same unique subject identification number throughout the study.

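### The Induction SAP fills its CPK-elevation row of special interest with a muscle-disorder search, so the row does not count what its label says and differs from the Extension SAP

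*SAP*

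**What the plan says.** Protocol section 8.1.7.2.1 leaves the specification of AESIs to the SAP, so section 11.2.2 of each SAP is the working definition.

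**Induction SAP, 11.2.2.** The method sentence is "The Adverse Events of Special Interests (AESI) categories will be summarized and presented for each treatment group using SMQ/CMQ". No row of the table is defined by a preferred term or a laboratory value. The two rows at issue are:
- CPK: "Elevated creatine phosphokinase | SMQ | Narrow | 'Rhabdomyolysis/myopathy"
- Renal: "Increased serum creatinine and renal dysfunction | SMQ | Narrow | 'Acute renal failure"

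**Extension SAP, 11.2.2.** The method sentence adds preferred terms to the permitted searches, and the corresponding rows are:
- Muscle: "Rhabdomyolysis/myopathy | SMQ | Narrow | 'Rhabdomyolysis/Myopathy"
- CPK: "Creatine phosphokinase (CPK) Elevation | Preferred Term | | 'blood creatine phosphokinase increased"
- Renal: "Renal dysfunction | SMQ | Narrow | 'Acute renal failure"

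**Where the rows feed.** Induction SAP 11.2.1 includes a line for any treatment-emergent AESI among the overview categories. It compares that line with placebo by Fisher's exact test; section 11.1 sets the two-sided level at 0.100. Extension SAP 11.2.1 has the same overview line for its own period and adds an overview for all subjects ever given ABT-494, which section 5.1 counts from Induction baseline.

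**The concern.** A reader of the Induction AESI table will take the CPK row as the number of subjects with a reported CPK rise. The row is instead the output of a query for rhabdomyolysis and myopathy. The sponsor's later plan treats the two as different events, and the Induction table was not set up that way.

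The Induction table matters because it is the only AESI table with a concurrent placebo group. Protocol section 5.5.3 states "At Week 16, all subjects will be re-randomized in a ratio of 1:1:1 to the three double-blind doses of ABT-494", so every later comparison is between active doses. Induction is also the only period in which 24 mg BID is a randomised arm. A mislabelled row here affects the one place where an AESI rate by dose can be set against placebo.

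The renal row raises a smaller version of the same question. Its label joins raised serum creatinine to renal dysfunction, but its only search is for acute renal failure. Protocol section 3.2 mentions creatinine when it describes tofacitinib ("in some subjects and also increased serum creatinine"), so a reader may look for creatinine events in that row.

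**Working it through.** No power, event count or rate is at issue, and the plan gives no figure to reproduce. The check sets label against search in each SAP and then follows the row into the overview.

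1. **CPK label against search, Induction.** The label is a laboratory finding. The search is one narrow standardised query named for a muscle disorder. There is no preferred-term or laboratory criterion.

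2. **The same search in the Extension SAP.** The same-named narrow query appears under a label that matches it, and CPK elevation has its own row with a different kind of search. One search thus carries two different labels across the two SAPs.

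3. **Does the mismatch depend on what the query contains?** Neither SAP gives its term list, so both cases have to be taken.
   - If the query does not include the CPK preferred term, a reported CPK rise without a muscle-disease term is absent from the row that bears its name.
   - If the query does include that term, the row mixes CPK rises with muscle-disease events and reports them all as CPK elevation.

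   In either case the row is not a count of CPK elevation.

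4. **Effect on the any-AESI line.** In the first case, a subject whose only relevant event is a reported CPK rise is outside the Induction line but would be inside the Extension line. In the second case that subject is inside both, and the line does not change on this account. The definitions may therefore differ for this event; the documents do not settle whether they do. The same holds for the cumulative overview. A CPK event during Induction would count there under the Extension definition, whereas its status in the Induction overview is unknown.

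5. **Renal row.** The query is the same narrow acute-renal-failure search in both SAPs. It fits the second half of the Induction label. Nothing in the row searches for raised creatinine as such, and the Extension SAP drops that half of the label without adding a creatinine row. The counts are like for like; only the label is too broad.

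6. **Where else the events are analysed.** Induction SAP 11.2.1 specifies Fisher's exact tests for each preferred term, for each dose and for the pooled doses against placebo. Section 11.3 compares mean change from baseline with placebo at each time point by ANOVA with 95% confidence intervals, and gives shift tables for every chemistry parameter. CPK and creatinine are both on the chemistry panel (Protocol Table 2).

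**The case against.** The strongest reply is that this is a labelling fault in a secondary summary table, and that the same events are compared with placebo elsewhere. That stands. A CPK or creatinine signal would be visible by dose in the preferred-term tests and the laboratory ANOVA. Protocol section 6.1.1.1 treats a laboratory abnormality as an adverse event only under stated conditions, so measured values are in any case the main evidence for such rises. The protocol's own AESI list (section 8.1.7.2.1) names neither CPK nor creatinine, and section 6.1.7 has no CPK rule. Induction SAP 11.2.2 also allows further events to be tabulated, although at discretion.

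Several stronger readings are tempting, and the documents do not support them:
- A reader might infer that CPK rises are certainly missing from the Induction row, because the Extension SAP would not need a separate row if the muscle query already captured them. That does not follow. Both tables contain nested rows: the Induction table lists infection and also serious infection as a subset of it, and the Extension table lists malignancy and also malignancy without non-melanoma skin cancer. A separate row does not show that the searches do not overlap.
- A reader might infer that renal counts cannot be compared between Induction and Extension. They can, because the named query is the same.
- A reader might take the tofacitinib remark in Protocol 3.2 as a stated class effect. That section describes the rises as typically asymptomatic and reversible, and argues that JAK1 selectivity may lessen such concerns.

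The reply does not repair the row itself. Coverage elsewhere does not make the label true, nor does it align the any-AESI line between the two SAPs.

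**Conclusion.** The point holds in a limited form. The Induction CPK row does not count what its label says, whichever terms the query holds. The any-AESI comparison with placebo may therefore use a different definition from the Extension and cumulative overviews. The conclusion rests on the names of the searches in the two SAPs and on the Extension SAP's own separation of the two events.

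No size can be given. The query's term list is not in the documents and neither are event rates, so any percentage would be assumed rather than derived. The effect is confined to one AESI row and possibly the overview line. It is misclassification in a summary table, not loss of a safety signal. The renal point is secondary and concerns only the label.

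**What to change.** In Induction SAP 11.2.2:
1. Count CPK elevation by the preferred term already used in the Extension SAP.
2. Show the narrow muscle query as a row of its own, under its own name.
3. Relabel the renal row as renal dysfunction, as the Extension SAP does. A separate creatinine row by preferred term is optional; neither SAP has one.
4. State one AESI definition for the any-AESI line in the Induction, Extension and cumulative overviews. The two tables differ in other rows as well: for example, overall infection appears only in the Induction table, lymphopenia only in the Extension table, and the perforation searches differ. A common definition has to settle those rows too.

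Extension SAP section 3.0 places the Induction database lock in December 2016. If the Induction outputs are final, provide the revised AESI table and overview line as a supplement, labelled as such, and leave the original tables in place. The cost is a few lines of SAP text and a rerun of the AESI table and the overview line, from data already collected.
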